# 8.3 ADVERSE EVENTS AND SERIOUS ADVERSE EVENTS

# 8.3.1 DEFINITION OF ADVERSE EVENTS (AE)

Adverse event means any untoward medical occurrence associated with the use of an intervention in humans, whether or not considered intervention-related (21 CFR 312.32 (a)).

Complications associated with standard administration of hypothermic protocol could lead to prolonged hospitalization, permanent disability, permanent end organ damage or death. There may be other risks that are unknown at this time. All safety events will be collected and reviewed throughout the entire trial periodically. The Investigator will notify the local IRB of any additional risks identified that could affect the health, safety or welfare of the trial patients.

# 8.3.2 DEFINITION OF SERIOUS ADVERSE EVENTS (SAE)

An adverse event (AE) or suspected adverse reaction is considered "serious" if, in the view of the investigator, it results in any of the following outcomes: death, a life-threatening adverse event, prolongation of existing hospitalization, a persistent or significant incapacity or substantial disruption of the ability to conduct normal life functions, or irreversible organ impairment. Important medical events that may not result in death or be life-threatening may be considered serious when, based upon appropriate medical judgment, they may jeopardize the participant and may require medical or surgical intervention to prevent one of the outcomes listed in this definition. Examples of such medical events include arrhythmia requiring intensive treatment and bleeding requiring transfusions or proven infection requiring initiation of antibiotics. The investigator must report any suspected adverse event that is serious as outlined to the local IRB.

# 8.3.3 CLASSIFICATION OF AN ADVERSE EVENT

### 8.3.3.1 SEVERITY OF EVENT

Potential Adverse events include impaired clotting and bleeding. Severity of bleeding will be graded based on the Bleeding Academic Research Consortium (BARC), standardized set of definitions for all bleeds.

Type 0 equals no bleeding

Type 1- Bleeding that is not actionable and does not cause the patient to seek or require treatment,

Type 2- any overt, actionable sign of hemorrhage, more bleeding that would be expected for the clinical circumstance, including bleeding found by imaging alone that does not fit the criteria for type 3, 4 or 5 but does not meet at least one of the following criteria:

Requiring non-surgical, medical intervention Leading to hospitalization or an increase level of care if currently hospitalized Prompting evaluation

Type 3a- overt bleeding plus hemoglobin drop of 3 to <5 g/dl Any transfusion with overt bleeding

- Type 3b- Overt bleeding plus hemoglobin ≥ 5 g/dl Cardiac tamponade Bleeding requiring surgical intervention for control Bleeding requiring intravenous vasoactive agents
- Type 3c- Intracranial hemorrhage Subcategories confirmed by imaging or lumbar puncture
  - Intraocular bleeding compromising vision

Type 4 Coronary Artery Bypass Graft (CABG) related bleeding Perioperative intracranial bleeding in 48 hours Reoperation after closure of sternotomy for the purpose of controlling bleeding Transfusion of ≥ 5 units of whole blood or packed red blood cells within a 48 hour period Chest tube output more than or equal to 2 liters within a 48 hour period

Type 5 fatal bleeding

Type 5a probably fatal bleeding (no autopsy or imaging confirmation) but clinically suspicious Type 5b definite fatal bleeding; overt bleeding or autopsy or imaging confirmation

Additional adverse events include increased chance of infection. Patients with an active bacterial or fungal infection superimposed on current COVID-19 infection are excluded from this study. New infections that develop post hypothermic protocol induction will be rated based on the following grading scale. Patients who develop new infection as documented by focal findings on physical exam, culture, blood work who respond to course of one treatment (anti-bacteria or antifungal agents) will be graded as mild; new infection that requires more than one antibacterial or antifungal, persistent or worsening findings beyond the typical course of the infection will be graded as moderate; severe infection will be defined as infection causing sepsis and organ failure requiring the use of supportive medications such as vasopressors, or additional means of support (additional changes in medication regimen targeted to infection, changes in ventilator management, or additional surgical procedures to treat infection for example thoracentesis for extensive infectious pleural fluid).

For adverse events (AEs) not included in the protocol defined grading system, the following guidelines will be used to describe severity.

• **Mild** – Events require minimal or no treatment and do not interfere with the participant's daily activities.

- **Moderate** Events result in a low level of inconvenience or concern with the therapeutic measures. Moderate events may cause some interference with functioning.
- Severe Events interrupt a participant's usual daily activity and may require systemic drug therapy or other treatment. Severe events are usually potentially life-threatening or incapacitating. Of note, the term "severe" does not necessarily equate to "serious".

Adverse Events of bradycardia, a known arrhythmia and adverse event of hypothermia, will also be rated based on above mild/moderate and severe scale. Other arrhythmias will be rated based on above criteria of mild/moderate and severe scale. Adverse events of reduced blood pressure or hemodynamic instability will be defined as a mean arterial pressure of less than 60 mmHg that is not stable and requires vasoactive pressors support. It will be graded as mild if no treatment required and mean arterial pressure returns to normal, moderate if it persists and a vasoactive medication initiated and severe if more than one vasoactive pressor is initiated and is worsening in nature requiring a halt of the hypothermic protocol.

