# 6.5.1 RESCUE MEDICINE

Routine FDA approved medications for pain and sedation, such as Fentanyl, Dilaudid, Versed, Ketamine or Precedex may be administered to make the subject more comfortable during the course of cooling and to treat any shivering. These medications will be administered through an intravenous line. Expected body reactions to cooling include shivering and administration of such medications would not be considered treatment for an adverse event.

A paralytic infusion such as cisatracurium or rocuronium may rarely be necessary for shivering. A lot of patients, however, are already paralyzed due to their critical illness.

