# 7.2 PARTICIPANT DISCONTINUATION/WITHDRAWAL FROM THE STUDY

Participants are free to withdraw from participation in the study at any time upon request. An investigator may discontinue or withdraw a participant from the study for the following reasons:

- If any clinical adverse event (AE), laboratory abnormality, or other medical condition or situation occurs such that continued participation in the study would not be in the best interest of the participant
- Disease progression which requires discontinuation of the study intervention
- If the participant meets an exclusion criterion (either newly developed or not previously recognized) that precludes further study participation
- Participant unable to receive hypothermia protocol for 48 hours

The reason for participant discontinuation or withdrawal from the study will be recorded on the Study Withdrawal Case Report Form (CRF).

The hypothermia protocol will be discontinued and full rewarming will be initiated prior to 48 hours if the following conditions occur: (1) hemodynamically unstable arrhythmia, (2) severe bradycardia (< 40bpm), (3) MAP less than 60mm Hg while on more than one vasopressor after resuscitation, (4) severe bleeding.

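### The general AE severity scale uses a daily-activity criterion that cannot discriminate in ventilated patients and has no link to halting hypothermia, so bradycardia below 40 bpm that stops cooling can be graded mild

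*Combined protocol and SAP*

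**What the plan says.** Section 8.3.3.1 gives bleeding (BARC types), infection and hypotension their own grading criteria. The rest go to a general three-level scale: "For adverse events (AEs) not included in the protocol defined grading system, the following guidelines will be used to describe severity". Two event types are sent there by name: "Adverse Events of bradycardia, a known arrhythmia and adverse event of hypothermia, will also be rated based on above mild/moderate and severe scale", and "Other arrhythmias will be rated based on above criteria of mild/moderate and severe scale". Electrolyte abnormalities and the skin injuries from cooling pads listed in 2.3.1 are not named, so the default clause catches them.

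The definitions are:
- At the mild level: "Events require minimal or no treatment and do not interfere with the participant's daily activities".
- At the moderate level: "Events result in a low level of inconvenience or concern with the therapeutic measures", with some interference with functioning as a possibility.
- At the severe level: events interrupt the participant's "usual daily activity and may require systemic drug therapy or other treatment". A further sentence says such events usually threaten life or incapacitate.

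None of the three levels mentions a heart rate or the stopping of hypothermia.

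Section 7.2 lists, among the reasons for ending cooling early, "severe bradycardia (< 40bpm". Section 10.1.6 repeats that trigger with the same label, and adds electrolyte abnormalities that do not respond to treatment. Every participant is mechanically ventilated (5.1, criterion 5), and 6.5.1 notes: "A lot of patients, however, are already paralyzed due to their critical illness".

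**The concern.** A grading criterion is useful only if it can take different values for different events. In this population, interference with daily activity takes one value for everyone. It therefore cannot separate mild from severe, and the leading element of the severe definition cannot be met on a literal reading.

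The grade is also cut off from the protocol's own judgement of what is grave enough to end cooling. The same heart-rate event is labelled severe in two sections and may be recorded as mild under a third.

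Section 10.1.6 names four risks as the primary concern: coagulopathy, infection, arrhythmia and electrolyte abnormality. Bleeding and infection have their own criteria; arrhythmia and electrolyte abnormality depend on the general scale. At stake are the severity entries on the case report form, the duration at each severity level that 8.3.4 wants to be assessable, any tabulation by severity under 9.4.4, and the expectedness decision in 8.3.3.3, which uses severity.

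**Working it through.** The plan gives no figure to reproduce, so the check sets the definitions beside the stopping conditions.

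**Step 1. Which scale is meant.** The arrhythmia sentences refer to a scale above them. Two mild/moderate/severe scales precede them, one for infection and the general one. The infection scale is worded around antimicrobial treatment and sepsis, so the general scale is the only workable reading.

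**Step 2. Which events on that scale stop cooling.** There are three: bradycardia below 40 bpm (7.2 and 10.1.6), haemodynamically unstable arrhythmia (7.2 and 10.1.6), and refractory electrolyte abnormality (10.1.6 only).

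**Step 3. Apply each part of the definitions.** Mild has two conditions joined by *and*: little or no treatment, and no interference with daily activities. The second is met trivially by a ventilated patient, so the first decides.

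| Event that stops cooling | Little or no treatment? | Life-threat wording of severe | Can it be graded mild? |
|---|---|---|---|
| Bradycardia <40 bpm, recovers on rewarming alone | Yes, if rewarming is not counted as treatment | Left to the rater | Yes |
| Haemodynamically unstable arrhythmia | Hard to support: 10.1.6 says arrhythmias are treated to ICU standard | Fits readily | Largely blocked |
| Refractory electrolyte abnormality | No: treatment was given and failed | Left to the rater | Blocked on a plain reading |

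So one of the three can clearly be graded mild while ending cooling.

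**Step 4. Compare with hypotension in the same paragraph.** There, mild needs no treatment, moderate means a vasoactive drug was started, and severe means more than one was started with worsening that requires hypothermia to be halted. Each level uses something observable in a ventilated patient, and the top level is tied to halting hypothermia. The general scale lacks both features.

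**Step 5. What the grade reaches.** Severity is recorded on the case report form (8.3.4) and enters the expectedness judgement (8.3.3.3). Section 9.4.4 promises summary statistics for safety endpoints without naming severity. The stopping triggers in 7.2 and 10.1.6 are direct clinical findings, and seriousness in 8.3.2 is defined by outcome and medical judgement. Neither uses the grade.

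**Step 6. Size.** With 20 enrolled (9.2), regrading one participant moves a severe-event proportion by 1/20 = 5 percentage points. This is the granularity of the study, not an estimate of misgrading. The documents give no expected incidence of bradycardia or any other event.

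**The case against.** The strongest reply is that the scale does not rest on daily activity alone. Mild also requires little or no treatment, moderate refers to concern with therapeutic measures, and severe carries the life-threat sentence. A sensible ICU clinician would use those parts and grade a heart rate below 40 as severe. This stands in part. It means the scale permits a mild grade for that event but does not compel one, and it largely disposes of the other two stopping events.

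Second, participants' protection does not run through this grade. Arrhythmia needing intensive treatment is an SAE example at any grade (8.3.2), 8.3.3.1 itself separates severe from serious, and SAEs go at once to the investigator and the DSMB (10.1.6). The safety report described in 10.1.6 covers events and actions taken, so a stop to cooling should be visible there however it is graded. All of this stands.

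Third, tying severity to a stopping condition mixes intensity with action taken. That is a fair point of principle, but the protocol already does so for hypotension and already labels bradycardia below 40 bpm as severe.

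A reader might also infer that the reference to systemic drugs lets a routine intravenous electrolyte replacement be graded severe. The text does not support this. Drug therapy is only a possible accompaniment to interrupted daily activity; it is not sufficient on its own.

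**Conclusion.** The point holds in a limited form. The daily-activity criterion does no work in this population, the general scale is not linked to the stopping conditions, and 8.3.3.1 is inconsistent with 7.2 and 10.1.6 for bradycardia below 40 bpm that recovers on rewarming alone. That case rests on two assumptions: early rewarming does not count as treatment, and the rater does not judge the event a threat to life. The documents settle neither.

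Three stronger readings are tempting and are not supported:
- That any arrhythmia or electrolyte event that stops cooling can be graded mild. The treatment and life-threat wording largely prevents this outside bradycardia.
- That these events have no usable grade, or that all 20 participants are affected. The other parts of the definitions still function, and only participants who have an event on this scale are touched.
- That the grades drive DSMB decisions. No section says that severity grades go to the DSMB, and 10.1.6 leaves its data elements to the charter.

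The consequence is confined to the severity record, its summaries and the expectedness judgement. It should be corrected, but it does not threaten the study's safety rules.

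**What to change.** Reconcile 8.3.3.1 with 7.2 and 10.1.6. For bradycardia, other arrhythmias, electrolyte abnormalities, skin injury and any other event without its own scale, replace the daily-activity wording with levels anchored as hypotension already is:
- Mild: no or minimal new treatment, no threat to life, no stopping condition met.
- Moderate: more than minimal new treatment, no threat to life, no stopping condition met.
- Severe: a threat to life, or one of the protocol's existing stopping conditions met.

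Define minimal treatment, and state whether routine electrolyte replacement counts as such. Whether rewarming is treatment then no longer matters, because an event that meets a stopping condition is placed by that fact. Refer to the stopping conditions by section, and reconcile the two lists, since the electrolyte condition appears in 10.1.6 but not in 7.2. No clinical threshold or stopping rule changes.

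The cost is one rewritten paragraph, a changed pick-list on the AE form, and IRB approval of the amendment. No new data are needed: heart rate, medications and the course of cooling are already documented (6.4), an ECG is taken for bradycardia or new arrhythmia (8.2), and electrolytes are measured every 12 hours (10.1.6).

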## 5.2 EXCLUSION CRITERIA

An individual who meets any of the following criteria will be excluded from participation in this study:

- 1. Bleeding (active bleeding, platelets less than 50,000)
- 2. Uncontrolled cardiac arrhythmia
- 3. History of cryoglobulinemia, major trauma, pregnancy
- 4. Active non-COVID-19 infection that is not controlled with antibiotic or antifungal regimen

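### Hypotension is graded by pressors started on study but cooling stops by pressors in use, so some events that end cooling are graded moderate or fit no grade

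*Combined protocol and SAP*

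**What the plan says.** Section 8.3.3.1 defines the event as a "mean arterial pressure of less than 60 mmHg that is not stable and requires vasoactive pressors support". It then sets three grades:

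- Mild: "graded as mild if no treatment required and mean arterial pressure returns to normal".
- Moderate and severe: "moderate if it persists and a vasoactive medication initiated and severe if more than one vasoactive pressor is initiated and is worsening in nature".
- The severe clause in full: "severe if more than one vasoactive pressor is initiated and is worsening in nature requiring a halt of the hypothermic protocol".

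Section 7.2 lists the conditions under which cooling ends before 48 hours. The third is "3) MAP less than 60mm Hg while on more than one vasopressor after resuscitation".

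Three other provisions matter:

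- The exclusion list opens "An individual who meets any of the following criteria will be excluded from participation in this study". No item in it, including the calorimetry item that runs into the heading of Section 5.3, mentions vasopressors. Section 5.1 does not limit them either.
- Section 8.3.4 treats conditions present at screening as baseline. It requires deterioration during the study to be recorded as an adverse event, and it makes severity part of the adverse event record.
- The general mild, moderate and severe scale in 8.3.3.1 is introduced by "For adverse events (AEs) not included in the protocol defined grading system, the following guidelines will be used to describe severity". Hypotension has its own scale.

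**The concern.** The two sections describe the same clinical state but count different things. Section 7.2 counts all agents in use, whenever they were begun. Section 8.3.3.1 counts agents *initiated*. The counts agree only for a patient who enters on no pressor.

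The study enrols ventilated, critically ill patients, and pressor support at entry is allowed. If such a patient deteriorates, Section 8.3.4 requires an adverse event with a severity. The severe category refers to halting cooling, so it appears meant to match the stop rule, but its drug count does not. At stake is whether the recorded severity of hypotension that ends cooling means the same thing for every patient in a 20-patient, single-arm pilot.

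**Working it through.** The plan states no figure on this point, so there is none to reproduce. The check applies the two rules as logic.

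**Inputs.** Let b be the pressors running at entry and k the pressors started on study. Consider MAP below 60 mmHg that persists after resuscitation.

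- Stop condition (7.2, condition 3): met when b + k > 1.
- Grade as written (8.3.3.1): severe when k > 1 and the event is worsening; otherwise moderate when k ≥ 1; no moderate or severe grade when k = 0.
- Mild is not available, because it needs no treatment and a return to normal pressure.

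**Worsening events, up to three pressors in total, stop condition met:**

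| At entry (b) | Started (k) | In use (b + k) | Grade as written |
|---|---|---|---|
| 0 | 2 | 2 | severe |
| 0 | 3 | 3 | severe |
| 1 | 1 | 2 | moderate |
| 1 | 2 | 3 | severe |
| 2 | 0 | 2 | none fits |
| 2 | 1 | 3 | moderate |
| 3 | 0 | 3 | none fits |

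Five rows have b ≥ 1. Four of them are graded moderate or not graded. These are logical combinations, not patients, and the documents attach no frequency to any of them.

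**Counting b + k in place of k.** All seven rows have b + k > 1, so all seven become severe.

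**Events that are not worsening.** The severe grade also requires worsening, which 7.2 does not. If the event meets the stop condition without worsening, none of the seven rows reaches severe, and counting b + k does not change that. Aligning the count alone therefore leaves a second gap, which also affects patients who enter on no pressor.

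**The case against.** The strongest reply is that this is the most literal reading available. The word *initiated* carries no time window, so a grader could count a pressor begun before enrolment. Severity is a clinician's assessment, and someone who has just stopped cooling for low pressure on two pressors has a clear cue to choose severe. An event that fits no hypotension grade might be moved to the general scale.

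These readings are possible, but the text does not state any of them. The baseline rule in 8.3.4 points towards changes on study, and the general scale is reserved for events outside the protocol-defined system. Two careful graders could record the same event differently.

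The objection does limit the consequences. A reader might infer that the DSMB would be misled about safety, but the documents do not support that. Section 10.1.6 has the DSMB report cover actions taken, so a halt of cooling is visible, and has serious events reported to the DSMB immediately. Section 8.3.6 sends it events defined by seriousness, and 8.3.3.1 itself separates severe from serious. Section 9.4.4 promises summary statistics only; no severity table is described. Section 9.4.8 lists individual data.

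**Conclusion.** The concern holds as an inconsistency between Sections 7.2 and 8.3.3.1 that can understate the recorded severity of some hypotension events that end cooling. It rests on two readings: that *initiated* means started on study, and that the general scale does not cover hypotension. Both follow the wording most closely.

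Its size in patients cannot be computed. The documents give neither the share of patients on a pressor at entry nor the rate of hypotension during cooling. The patients affected are only those who enter on a pressor and then reach the stop condition, plus any who reach it without worsening.

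Two stronger conclusions might be inferred, and neither is supported:

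- That nobody who enters on a pressor can be graded severe. A patient who enters on one and has two added, with a worsening event, is graded severe.
- That a given fraction of the 20 patients would be misgraded. Any such figure would need an assumed rate of pressor use at entry, and would count patients exposed to the flaw rather than events misgraded.

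The stop rule operates without the grade, and SAE reporting follows seriousness. The effect is confined to how severity is recorded and summarised.

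**What to change.** Sections 8.3.3.1 and 7.2 must be reconciled. Two statements in 8.3.3.1 would do it:

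1. The hypotension grade takes account of all pressors in use, including those running at the start of cooling.
2. Any hypotension for which cooling is stopped under Section 7.2, condition 3, is recorded as severe.

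The second statement is needed because of the separate worsening requirement. The fix concerns classification only; the clinical stop condition stays with the sponsor. The same rewrite could settle a neighbouring inconsistency: the event is defined as requiring pressor support, while the mild grade requires no treatment.

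The cost is protocol wording. Concomitant medication is scheduled from screening/baseline (Section 1.3) and medication during cooling is documented (Section 6.4), so no new data are needed. The small downside is that a few more events will be recorded as severe.
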